6.2 DETAILS OF TRIAL PROCEDURES AT SELECTED VISITS

Study procedures to be performed at each visit are listed in the [Flow Chart](#) and the respective protocol sections. Refer to [Section 5](#) and the [Appendix Section 10](#) for explanations of procedures. Additional details on procedures at selected visits are provided below.

Measurement of vital signs should precede blood sampling and be assessed pre-dose at dosing visits.

Self-administered patient questionnaires (DLQI, WLQ) should be completed by the patient on his/her own in the pre-specified order in a quiet area/room before any other visit assessments or treatments, and, if possible, before any interaction with the investigator or other members of the study team.

The quality of life questionnaires (DLQI and WLQ) are self-administered by the patient using an electronic device. Also the Questionnaires to be completed by study site personnel (PASI, sPGA, NAPSI, PPASI, PSSI, HCRU, and the BI 655066 (active or placebo) self-administration questionnaire) will be completed using an electronic device, after the DLQI and WLQ have been completed by the patient. All questionnaires are detailed in [Appendix 10](#).

6.2.1 Screening period

After patients have been informed about the trial, written informed consent in accordance with GCP and the local legislation must be obtained prior to performing any study related procedures. A separate informed consent is required for optional study procedures which are DNA banking from blood samples, biomarker serum sample banking, skin biopsies and biomarker tissue sample banking from skin biopsies.

Once they have consented, the patient is considered to be enrolled in the trial and have started screening. The patient should be recorded on the enrolment log and be registered in IRT as a screened patient. Patients will be assigned a patient number and enrolment must be recorded in the eCRF pages.

Screening (Visit 1) should normally take place no more than 42 days before Visit 2 and be completed no less than 7 days prior to Visit 2. Screening procedures may be extended to more than 1 physical visit, if needed.

Re-screening will not be permitted. Patients who fail screening following Visit 1 assessments should be registered as a screen failure in IRT.

For the comprehensive list of the trial procedures required at the Screening Visit (Visit 1) please refer to [flow chart](#).

Infection screening

[See table 5.3.3: 1](#) for the list of infection screening tests that will be performed to verify exclusion criteria. Instructions regarding sample collection, sample handling/processing and sample shipping are provided in the Laboratory Manual in the ISF. See exclusion criteria [Section 3.3.3](#) with study participation directive for patients with a positive QuantiFERON® or PPD skin test for TB.

Demographics

Informed consent date, HIPAA status (US patients only), sex, ethnicity and race (if allowed by local law) will be collected and reported in the eCRF. The patient's smoking and alcohol history will also be assessed.

Medical History

Cardiovascular (CV) History and CV risk factors will be collected and reported in the Medical History eCRF page.

Baseline Conditions

Chronic diseases, current observable conditions, any new clinically relevant findings discovered from the physical examination, ECG, safety labs, and any condition requiring therapy (excluding psoriasis) will be reported on the Baseline Condition eCRF page.

IRT

All patients that are screened must be registered with IRT. If the patient results in a screen failure, IRT should be notified as soon as possible and within the 42 day screening period. Details of IRT procedures can be found in the IRT manual located in the ISF.

6.2.2 Treatment period

The treatment period is from Visit 2 to End of Treatment (EOT) Visit.

Safety laboratory testing

Visits 2, 5, 8, 11, EOT and EOO should be performed in fasted state (8 hours no food and only water). This is not necessary at the Screening Visit. If a patient comes in non-fasted where a fasting condition is required, the visit should be performed, the non-fasted condition documented on the laboratory requisition, and the patient reminded about the expected conditions.

Pregnancy testing

Urine pregnancy testing for all woman of child-bearing potential will be conducted on-site approximately every four weeks and must be negative to further treat the patient. The pregnancy testing should be done prior to administration of study drug. A positive urine test must be confirmed with a serum pregnancy test.

Randomization via IRT and administration of study medication should be the last activity at Visit 2.

Skin biopsies should be collected prior to administration of study drug at dosing visits.

Venipuncture (i.e. safety laboratories, PK, ADA, biomarkers) should be the last procedure prior to any study drug administration. On dosing visits PK and ADA samples should be taken approximately within 1 hour prior to administration of study drug.

Patients should be closely monitored for signs and symptoms of hypersensitivity reactions for approximately 2 hours after the last injection at the Randomization Visit (Visit 2) and approximately 1 hour after the last injection at all other drug administration.

6.2.3 Follow Up Period and Trial Completion

For all randomized patients termination of trial medication and trial completion must be recorded on the corresponding eCRF.

6.2.3.1 Early treatment and trial termination

If study medication is discontinued prior to the planned [Flow Chart](#) visit EOT, every effort should be made to have the patient continue in the trial and complete all of the remaining trial visits and procedures including EOT and EOO Visit; with the EOO Visit to be performed 4 weeks after the EOT Visit.

If a patient cannot or will not continue in the trial, the patient should complete EOT Visit procedures instead of the next planned treatment period visit. These patients should be registered as prematurely discontinued in IRT and return to the clinic for End of Observation Visit 16 (± 1) weeks after their last administered dose of BI 655066 (active or placebo). Patients who discontinue from the trial prematurely will not have the option to participate in the open label extension (OLE) study.

6.2.3.2 Trial completion

Patients who complete the randomized treatment period and who qualify for the open-label extension (OLE) study will continue treatment with active BI 655066 and therefore will not have a Follow-up Visit in study 1311.30.

6.2.3.3 Vital Status

Randomised patients who do not participate in the OLE study and who withdraw from the study prior to their planned EOO Visit will be contacted for their vital status assessment

(alive / dead / lost to follow-up). In case the patient died, an SAE form should be completed by the site and forwarded immediately to the sponsor. Vital status assessment should occur at 48 (\pm 1) weeks after randomisation.

7. STATISTICAL METHODS AND DETERMINATION OF SAMPLE SIZE

7.1 STATISTICAL DESIGN - MODEL

This is a confirmatory, multicenter, randomized, double-blind and active comparator controlled 44 week study evaluating the efficacy and safety of BI 655066 in patients with moderate to severe chronic plaque psoriasis. The primary objective of this trial is to assess the safety and efficacy of BI 655066 in comparison to adalimumab in patients with moderate to severe chronic plaque psoriasis. The primary efficacy evaluation will be assessed at 16 weeks comparing treatment with BI 655066 to adalimumab. The study will also evaluate the efficacy of treatment with BI 655066 following insufficient or only partial response with adalimumab.

Baseline refers to the measurement recorded at randomisation (Visit 2); if data at Visit 2 is missing, then data from Visit 1 will be considered baseline. The percent reduction from baseline is calculated by % PASI reduction from baseline = $((\text{PASI at baseline} - \text{PASI at Visit X}) / \text{PASI at baseline}) * 100$, at all follow up visits. Achieving an x% or larger reduction from baseline PASI score is denoted as PASI X.

Randomization will be stratified by weight (≤ 100 kg vs. >100 kg) and prior exposure to TNF antagonists (0 vs. ≥ 1). Based upon these design considerations and the binary nature of the co-primary endpoints of PASI 90 and sPGA 0 or 1, the trial will be analysed using the Cochran-Mantel-Haenszel risk difference estimate stratified by the randomisation factors mentioned previously.

7.2 NULL AND ALTERNATIVE HYPOTHESES

The primary hypotheses are that BI 655066 is different than adalimumab in achieving $\geq 90\%$ reduction from baseline in the Psoriasis Area and Severity Index score (PASI 90) and sPGA score of clear(0) or almost clear(1) at Week 16 in participants with moderate to severe chronic plaque psoriasis. For the primary analyses, this study has 2 treatment arms (BI 655066 and adalimumab [refer to [Figure 3.1: 1](#)]).

- Arm 1 – Patients randomised at Visit 2 to receive 150mg BI 655066 at Randomisation (Visit 2), Week 4 and then q12 weeks
- Arm 2 – Patients randomised at Visit 2 to receive 80mg adalimumab at Randomisation (Visit 2) and then 40mg adalimumab at Week 1 and then every other week

For the second part of the trial, patients randomised to receive adalimumab at Visit 2 and achieve a PASI 50 response but not PASI 90 at Week 16 will be re-randomised to one of the following treatment arms:

Arm A – Patients re-randomised to receive BI 655066 during the remaining treatment period of the trial

Arm B – Patients re-randomised to continue to receive adalimumab during the remaining treatment period of the trial

The following null hypotheses will be tested in a hierarchical order using two-sided tests with a type I error of 0.05. The co-primary endpoints need to be significant simultaneously, therefore no alpha adjustment is necessary.

1. BI 655066 arm (Arm 1) is not different from adalimumab (Arm 2) with respect to PASI 90 or sPGA score of clear or almost clear (0 or 1) response at Week 16
2. BI 655066 arm (Arm 1) is not different from adalimumab (Arm 2) with respect to PASI 75 response at Week 16
3. BI 655066 arm (Arm 1) is not different from adalimumab (Arm 2) with respect to PASI 100 response at Week 16

For the re-randomised patients, the following null hypothesis test will be performed with a type I error of 0.05.

- BI 655066 arm (Arm A) is not different from adalimumab (Arm B) with respect to PASI 90 response at Week 44 for patients who are re-randomized at Week 16.

7.3 PLANNED ANALYSES

The efficacy analyses will be based on the intent-to-treat principle, comprising all participants who were randomised and received at least one dose during the trial. Misrandomized patients are by definition screening failures and therefore are not included in the intended to treat population. Efficacy analyses will be based on the planned treatment (i.e., the treatment assigned at randomization); this set of patients is called the Full Analysis Set (FAS). Safety analyses will be based on the actual treatment received at the Randomization Visit; this set of patients is called the Safety Set (SAF).

Important violations of the protocol will include key inclusion and exclusion violations, incorrect medications taken, compliance with study medication, incorrectly re-randomized or not re-randomized, concomitant use of restricted medications, and any other violations of the protocol deemed important by the study team. All decisions concerning important protocol violations will be made prior to unblinding of the database. A per-protocol set (PPS) will be defined excluding patients with violations that affect Week 16 efficacy. A secondary re-randomized per-protocol set (RRS-PPS) will be defined excluding those patients with violations affecting the patients included in the Week 44 assessment of re-randomization. The hypothesis tests as described in [Section 7.2](#) will be repeated on the PPS or RRS-PPS populations, as appropriate.

7.3.1 Primary endpoint analyses

The achievement of PASI 90 at Week 16 is the first co-primary endpoint and is a binary variable with values of 0 or 1. The difference in proportion responding between the BI 655066 arm and the adalimumab arm will be estimated and tested using the Cochran-Mantel-Haenszel risk difference estimate stratified by the randomisation factors of weight (≤ 100 kg

vs. >100 kg) and prior exposure to TNF antagonists (0 vs. ≥1) with weights proposed by Greenland & Robins, which is calculated as follows:

$$\hat{\delta}_{MH} = \frac{\sum_{i=1}^u w_i \cdot \hat{\delta}_i}{\sum_{i=1}^u w_i}, \text{ where}$$

$$\hat{\delta}_i = \frac{x_i}{n_i} - \frac{y_i}{m_i} \text{ denotes the risk difference in stratum } i, i = 1, \dots, u$$

$$w_i = \frac{n_i \cdot m_i}{n_i + m_i} \text{ denotes the weight of stratum } i, i = 1, \dots, u$$

x_i denotes the number of patients with event in treatment₁ in stratum $i, i = 1, \dots, u$

y_i denotes the number of patients with event in treatment₂ in stratum $i, i = 1, \dots, u$

n_i denotes the number of patients on treatment₁ in stratum $i, i = 1, \dots, u$

m_i denotes the number of patients on treatment₂ in stratum $i, i = 1, \dots, u$

The estimated variance of $\hat{\delta}_{MH}$ is calculated as:

$$\widehat{var}(\hat{\delta}_{MH}) = \frac{\sum_{i=1}^u L_i}{(\sum_{i=1}^u w_i)^2}$$

$$\text{where } L_i = \frac{x_i(n_i - x_i) m_i^3 + y_i(m_i - y_i) n_i^3}{n_i \cdot m_i \cdot (n_i + m_i)^2}, i = 1, \dots, u$$

Assuming a normal distribution of $\hat{\delta}_{MH}$, an approximate 95% CI is given as follows, where $z_{0.975}$ is the 97.5% quantile of the standard normal distribution:

$$CI = \left[\hat{\delta}_{MH} \pm z_{0.975} \cdot \sqrt{\widehat{var}(\hat{\delta}_{MH})} \right]$$

Also, the approximate p-value can be calculated using the following:

$$pvalue = 2 \cdot \Pr \left[Z > \left| \frac{\hat{\delta}_{MH}}{\sqrt{\widehat{var}(\hat{\delta}_{MH})}} \right| \right], \text{ where } Z \sim N(0, 1)$$

If there is a stratum for a treatment group that has 0 patients in it, the 0 count will be replaced by 0.1 in order to prevent dividing by 0 in the above equations, as suggested in Greenland & Robins. Comparisons of the BI 655066 arm and adalimumab arm will include both a p-value and 95% confidence interval.

The achievement of a sPGA score of clear or almost clear at Week 16 is the second co-primary endpoint and is a binary variable with values of 0 or 1. The analysis of the sPGA co-primary endpoint will be identical to that of the PASI 90 co-primary endpoint detailed above.

7.3.2 Secondary endpoint analyses

Key secondary endpoints:

The achievement of PASI 75 at Week 16 is a binary variable with values of 0 or 1. The analysis of this endpoint will be identical to that of the PASI 90 co-primary endpoint detailed in the [Section 7.3.1](#).

The achievement of PASI 100 at Week 16 is a binary variable with values of 0 or 1. The analysis of this endpoint will be identical to that of the PASI 90 co-primary endpoint detailed in the [Section 7.3.1](#).

The achievement of PASI 90 at Week 44 is a binary variable with values of 0 or 1. The analysis of this endpoint will be identical to that of the PASI 90 co-primary endpoint detailed in the [Section 7.3.1](#). Note that this endpoint will only be analysed for patients who are re-randomized at Week 16 (i.e., only for Arm A and Arm B defined in [Section 7.2](#)).

Other secondary endpoints:

Other secondary endpoints will be summarized descriptively.

7.3.3 Further endpoint analyses

Further endpoints will be summarized descriptively, with number and proportion of responders for dichotomous endpoints and mean, median, SD and IQR presented for continuous variables.

Time to onset of *Endpoint*. The time to event will be calculated as:

- Time to first onset (with observed event) = [date of first onset] – [date of first active treatment] + 1
- If a patient never attains *Endpoint* (e.g. PASI 75 or PASI 90), then that patient's time to first onset will be censored at the last visit where the *Endpoint* was measured (e.g. PASI).

Time to Loss of *Endpoint* (from time of randomization), defined using the following algorithm:

- a) Never attains *Endpoint* (Failure at time 0)
- b) After achieving *Endpoint*, patient will be a failure if they subsequently do not achieve *Endpoint* and either discontinue from the study or switch therapy while still not achieving *Endpoint*. Time to failure will be calculated using date of first failure to achieve *Endpoint*.
- c) Patients that take prohibited meds to treat Psoriasis will be counted as failures at the time when they add the prohibited med.
- d) Patients that switch therapy while maintaining response will be censored at their last measurement prior to switching treatment.

- e) Patients who maintain *Endpoint* throughout the study will be censored at their last measurement.

Time to Loss of *Endpoint* (from time of achieving *Endpoint* or from specific point in time) will be defined as above but only for those patients that have achieved *Endpoint*.

All Time to Event endpoints will be presented using Kaplan-Meier curves with comparisons made between treatment groups using stratified Log-Rank test. If needed, further information will be provided in the TSAP.

7.3.4 Safety analyses

Adverse events will be coded using the Medical Dictionary for Regulatory Activities (MedDRA) coding dictionary. Standard AbbVie summary tables and listings will be produced. All adverse events with an onset between start of treatment and end of the residual effect period (REP), a period of 15 weeks after the last administration of BI 655066 (active or placebo), will be assigned to the treatment period for evaluation.

All treated patients will be included in the safety analysis. In general, safety analyses will be descriptive in nature and will be based on AbbVie standards. No hypothesis testing is planned.

Statistical analysis and reporting of adverse events will concentrate on treatment-emergent adverse events. To this end, all adverse events occurring between start of treatment and end of the residual effect period will be considered 'treatment-emergent'. The residual effect period is defined as 15 weeks. Adverse events that start before first drug intake and deteriorate under treatment will also be considered as 'treatment-emergent'.

Frequency, severity, and causal relationship of adverse events will be tabulated by system organ class and preferred term after coding according to the current version of the Medical Dictionary for Drug Regulatory Activities (MedDRA).

Laboratory data will be analysed both quantitatively as well as qualitatively. The latter will be done via comparison of laboratory data to their reference ranges. Values outside the reference range as well as values defined as clinically relevant will be highlighted in the listings. Treatment groups will be compared descriptively with regard to distribution parameters as well as with regard to frequency and percentage of patients with abnormal values or clinically relevant abnormal values.

Vital signs, physical examinations, or other safety-relevant data observed at screening, baseline, during the course of the trial and at the end-of-trial evaluation will be assessed with regard to possible changes compared to findings before start of treatment.

More information about the safety analysis will be provided in the TSAP.

7.3.5 Pharmacokinetic analyses

Descriptive statistics of BI 655066 concentration measurements by treatment group and visit will be provided.

Pharmacokinetic data will be analysed using population pharmacokinetic approaches. For this purpose, data may also be combined with data from other trials.

7.3.6 Pharmacodynamic analyses

No formal analysis of pharmacokinetic-pharmacodynamic relationships is planned. As the data from previous trials with BI 655066 suggest a pharmacokinetic (PK)-pharmacodynamic (PD) relationship for efficacy endpoints such as PASI, population PK-PD analyses will be performed. For this purpose, data may also be combined with data from other trials. Model-based analyses will be planned and documented separately according to internal and external guidelines and SOPs. Other exploratory analyses of drug concentration, biomarker or safety data may be performed using data obtained as part of this trial.

7.3.7 Biomarker analyses

Changes in serum protein, tissue protein and RNA biomarker levels over time will be described by treatment group. The details of these analyses will be included in the TSAP.

7.4 INTERIM ANALYSES

No interim analysis is planned for this study.

7.5 HANDLING OF MISSING DATA

Every effort should be made to collect complete data at all visits.

The following rules will be used to impute for missing data:

- For all non-binary endpoints, LOCF (Last Observation Carried Forward) will be used to impute missing values
- For all binary endpoints (i.e. endpoints that are either 1 (patient responded) or 0 (patient did not respond)):
 - If no data after that visit*, then impute as failure (NRI [No Response Imputation])
 - If data at visits* before and after, only impute as success if both visits are successes; else impute as failure.

* Patients that take prohibited medications to treat psoriasis will be treated the same as those that discontinued from the trial – i.e. subsequent visits following start of prohibited medication will be considered as failure for binary endpoints.

Missing items from the Quality of Life questionnaires will be handled according to the measure instructions (cf. [Appendix 10.6](#) and [10.7](#)). If there is no data for a particular visit, then it will be imputed following the same rules as described above.

Sensitivity analyses to assess the robustness of the hypothesis testing results will include:

- LOCF (for binary endpoints)
- Logistic regression
- MMRM (for continuous endpoints)
- Multiple imputation (for binary endpoints)

7.6 RANDOMISATION

At Visit 2, patients will be randomized in blocks to double-blind treatments, stratified by weight (≤ 100 kg vs. >100 kg) and prior exposure to TNF antagonists (0 vs. ≥ 1). Patients will be randomized to BI 655066 or adalimumab in a ratio of 1:1 within each level of stratification.

Patients originally randomized to BI 655066 150mg will stay on BI 655066 150mg. Patients who are originally randomized to adalimumab will be separated into three groups at Week 16 depending on their Week 16 PASI score. Patients will be switched to BI 655066 if they don't achieve PASI 50 at Week 16. Patients will continue on adalimumab if they achieve PASI 90 at Week 16. Patients will be re-randomized in a 1:1 ratio to either BI 655066 or adalimumab in a second double-blinded portion of the trial if they achieve PASI 50 but not PASI 90 at Week 16.

BI will arrange for the randomization and the packaging and labelling of trial medication. The randomization lists will be generated using a validated system, which involves a pseudo-random number generator so that the resulting treatment will be both reproducible and non-predictable. The block sizes will be documented in the CTR. Access to the codes will be controlled and documented.

7.7 DETERMINATION OF SAMPLE SIZE

This study is designed to show a benefit of BI 655066 over adalimumab in terms of PASI 90 response and sPGA scores of clear or almost clear at Week 16. This study is also powered to show a benefit in PASI 90 response at Week 44 between the patients randomized to continue on adalimumab vs patients randomized to BI 655066 at Week 16.

Based on the assumption that the Week 44 PASI 90 rate will be approximate 40% for adalimumab and 70% for BI 655066 for the patients who are re-randomized at Week 16, a total of 120 patients will result in $>90\%$ power for the key secondary objective of the trial using a type-I error rate at 5%. See [Table 7.7: 1](#) sample size calculations for different scenarios. Assuming for those patients originally randomized to adalimumab the response rate at Week 16 for PASI 90 and PASI 50 are 45% and 85%, respectively, then this leaves approximately 40% of patients expected to fall in the more than or equal to PASI 50 and less than PASI 90 range and thus be eligible for re-randomisation. This requires that 300 (40% of 300 = 120) patients be randomized to adalimumab at Randomisation.

Based on the outcome from the trials 1311.1 and 1311.2, the PASI 90 response rate at Week 16 is assumed to be at least 65% in the BI 655066 arm. For the primary analysis comparing BI 655066 to adalimumab, sample sizes of 300 per arm will allow for $> 90\%$ power assuming 70% and 50% PASI 90 response rates for BI 655066 and adalimumab, respectively. See [Table 7.7: 2](#) for more sample size calculations.

Table 7.7: 1 Sample sizes for 90% power for testing against adalimumab using PASI 90 at re-randomization

BI 655066 rate	adalimumab rate	Delta	Re-randomisation ratio BI 655066: adalimumab = Total N
65%	40%	25%	82:82 = 164
70%	45%	25%	80:80 = 160
70%	40%	30%	56:56 = 112
75%	45%	30%	54:54 = 108
80%	50%	30%	51:51 = 102

Table 7.7: 2 Sample sizes for 90% power for testing against adalimumab using PASI 90

BI 655066 rate	adalimumab rate	Delta	Randomisation ratio BI 655066: adalimumab = Total N
65%	50%	15%	226:226 = 452
70%	55%	15%	217:217 = 434
70%	50%	20%	124:124 = 248
75%	55%	20%	118:118 = 236
70%	45%	25%	80:80 = 160
75%	50%	25%	77:77 = 154

Based on the outcome from the trials 1311.1 and 1311.2, the achievement of sPGA clear or almost clear rate at Week 16 is assumed to be at least 85% in the BI 655066 arm. Assuming 70% rate for the adalimumab arm, by using the PASI 90 required sample sizes, 300 patients per treatment arm will provide at least 90% power for sPGA endpoint. See [Table 7.7. 3](#) for more sample size calculation.

As PASI 90 and sPGA are highly correlated, this trial will have >90% power for comparing BI 655066 arm to adalimumab arm on both of these endpoints.

Table 7.7. 3 Sample sizes for 90% power for testing against adalimumab using sPGA clear or almost clear

BI 655066 rate	adalimumab rate	Delta	Randomisation ratio BI 655066: adalimumab = Total N
85%	72.5%	12.5%	223:223 = 446
85%	70%	15%	161:161 = 322
87.5%	72.5%	15%	148:148 = 296
87.5%	70%	17.5%	113:113 = 226

Calculations were performed using ADDPLAN Version 6.0.4.

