4.3 Sample Size

This study is designed to show a benefit of risankizumab over adalimumab in terms of PASI 90 response and static Physician Global Assessment (sPGA) of clear or almost clear (sPGA of 0 or 1) at Week 16. This study is also powered to show a benefit in PASI 90 response at Week 44 between the subjects re-randomized to continue on adalimumab vs. subjects randomized to risankizumab at Week 16.

Based on the assumption that the Week 44 PASI 90 rate will be approximate 40% for adalimumab and 70% for risankizumab for the subjects who are re-randomized at Week 16, a total of 120 subjects will result in > 90% power for the primary efficacy analysis in Part B using a type-I error rate at 5%. See Table 1 sample size calculations for different scenarios. Assuming for those subjects originally randomized to adalimumab the response rate at Week 16 for PASI 90 and PASI 50 are 45% and 85%, respectively, then this leaves approximately 40% of subjects expected to fall in the more than or equal

to PASI 50 and less than PASI 90 range and thus be eligible for re-randomization. This requires that 300 (40% of 300 = 120) subjects be randomized to adalimumab at randomization.

Based on the outcome from Trials 1311.1 and 1311.2, the PASI 90 response rate at Week 16 is assumed to be at least 65% in the risankizumab arm. For the primary analysis comparing risankizumab to adalimumab, sample sizes of 300 per arm will allow for > 90% power assuming 70% and 50% PASI 90 response rates for risankizumab and adalimumab, respectively. See [Table 2](#) for more sample size calculations.

Table 1. Sample Sizes for 90% Power for Testing Against Adalimumab Using PASI 90 at Re-Randomization

Risankizumab	Adalimumab	Delta	Re-Randomization Ratio Risankizumab:Adalimumab = Total N
65%	40%	25%	82:82 = 164
70%	45%	25%	80:80 = 160
70%	40%	30%	56:56 = 112
75%	45%	30%	54:54 = 108
80%	50%	30%	51:51 = 102

Table 2. Sample Sizes for 90% Power for Testing Against Adalimumab Using PASI 90

Risankizumab	Adalimumab	Delta	Randomization Ratio Risankizumab:Adalimumab = Total N
65%	50%	15%	226:226 = 452
70%	55%	15%	217:217 = 434
70%	50%	20%	124:124 = 248
75%	55%	20%	118:118 = 236
70%	45%	25%	80:80 = 160
75%	50%	25%	77:77 = 154

Based on the outcome from Trials 1311.1 and 1311.2, the achievement of sPGA clear or almost clear rate at Week 16 is assumed to be at least 85% in the risankizumab arm.

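### The adalimumab Week 16 PASI 90 rate is 45% when the re-randomised pool is sized but 50% when the co-primary is powered; at 50% the expected pool is 105, below the plan's own 112

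*Protocol*

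**What the plan says.** Protocol 7.7 makes two power statements that both depend on the adalimumab PASI 90 rate at Week 16.

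- **Re-randomised comparison (Week 44 PASI 90).** The premise is that "the Week 44 PASI 90 rate will be approximate 40% for adalimumab and 70% for BI 655066" among re-randomised patients, and that "a total of 120 patients will result in" more than 90% power. To reach 120, the section assumes that on adalimumab "the response rate at Week 16 for PASI 90 and PASI 50 are 45% and 85%, respectively". The 40% lying between the two thresholds, applied to 300 patients, gives 120, and this is the stated reason for 300 in the adalimumab arm.
- **Co-primary comparison (Week 16 PASI 90).** The next paragraph claims more than 90% power with 300 per arm, "assuming 70% and 50% PASI 90 response rates for BI 655066 and adalimumab, respectively".

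Table 7.7: 1, titled "Sample sizes for 90% power for testing against adalimumab using PASI 90 at re-randomization", lists 56:56 = 112 in the 70% v 40% row. Table 7.7: 2, for the co-primary, lists adalimumab rates of 45%, 50% and 55%.

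SAP 4.3 repeats both sets of assumptions and all the tables. It raises the standing of the Week 44 test: the protocol calls it a key secondary objective, while the SAP says "a total of 120 subjects will result in > 90% power for the primary efficacy analysis in Part B". Neither document explains why the two Week 16 rates differ or shows how the pool changes with that rate.

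**The concern.** The adalimumab Week 16 PASI 90 rate is a single unknown, and a higher value hurts both comparisons. It narrows the Week 16 difference, and it removes patients from the re-randomised pool, because PASI 90 responders stay on adalimumab. The section takes the less favourable 50% where there is power to spare and the more favourable 45% where the margin is eight patients (120 against 112).

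At stake is the planned power of the Week 44 comparison. Under SAP 10.2 it is the Part B primary test, run independently at 0.05, and under SAP 10.3.1.2 the Part B PASI 100 test depends on it. Someone who accepts the 50% used for the co-primary should be able to carry it through to Part B and still find the stated power. They cannot.

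**Working it through.** **Inputs.** Week 44 rates 70% v 40%, 1:1 re-randomisation, 300 adalimumab patients, PASI 50 at 85%, and PASI 90 at 45% or 50% (Protocol 7.7 and 7.6). Type I error is 5%. The test is taken as two-sided: Protocol 7.2 says the Week 16 hypotheses are "tested in a hierarchical order using two-sided tests with a type I error of 0.05", Protocol 7.3.2 gives the Week 44 endpoint the same analysis as the co-primary, and SAP 10.1 sets a two-sided 0.05 level for efficacy.

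**Step 1: reproduce the plan's figure.** Pooled two-proportion formula, no continuity correction, n per arm:

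n = [z(0.975)·√(2p̄(1−p̄)) + z(0.90)·√(p₁(1−p₁)+p₂(1−p₂))]² / (p₁−p₂)²

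With p₁ = 0.70, p₂ = 0.40, p̄ = 0.55: √0.495 = 0.7036 and √0.45 = 0.6708, so

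n = [(1.960 × 0.7036 + 1.2816 × 0.6708)/0.30]² = 55.7, rounded up to 56 per arm, 112 in total.

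This matches Table 7.7: 1. The formula also reproduces the other four rows of that table and all six rows of Table 7.7: 2 to within one patient per arm. The unpooled formula gives (1.960 + 1.2816)² × 0.45/0.09 = 52.5, so 53 per arm, which is not the tabulated 56.

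**Step 2: pool size.** Pool = 300 × (0.85 − PASI 90 rate).

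**Step 3: power at 70% v 40%.** Pooled: Φ[(0.30√n − 1.960 × 0.7036)/0.6708]. Unpooled: Φ[0.30√n/0.6708 − 1.960].

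| Adalimumab Week 16 PASI 90 | Eligible share | Expected pool | Power, pooled | Power, unpooled |
|---|---|---|---|---|
| 45% (used to size the pool) | 40% | 120 | 92.1% | 93.4% |
| 50% (used for the co-primary) | 35% | 105 | 88.2% | 90.0% |
| 55% (also in Table 7.7: 2) | 30% | 90 | 82.8% | 85.1% |

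For the 50% row, n = 52.5: (0.30 × 7.2457 − 1.3790)/0.6708 = 1.185, and Φ(1.185) = 0.882. Exact enumeration of the unstratified unpooled test with 53:52 patients gives about 88.4%, so the 90.0% from the unpooled approximation is slightly optimistic.

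**Step 4: break-even values.** A pool of 112 needs an eligible share of 112/300 = 37.3%.

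- With PASI 50 at 85%, the pool falls below 112 once PASI 90 exceeds 85% − 37.3% = 47.7%.
- With PASI 90 at 50%, PASI 50 must be at least 50% + 37.3% = 87.3%.

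**Step 5: co-primary.** With 300 per arm, pooled power is 99.9% at 70% v 50% and above 99.9% at 70% v 45%. That claim stands under either rate.

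**The case against.** The strongest reply is that nothing here is miscalculated. The power statement is conditional on 120 patients, and 120 patients do give 92.1%. Taking 50% for the co-primary is also sound caution for that test. Both points stand: this is an inconsistency between inputs, not an arithmetic error. They do not answer the question of the pool, because caution about the adalimumab rate would point to 50% there too.

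A second reply is that the check moves one input and holds the rest. That is fair. PASI 50 might be above 85%, and the Week 44 rates might differ; a pool of 105 would meet the 80% v 50% row of Table 7.7: 1 (102). It would miss the 75% v 45% row (108), and 120 already misses both rows with a 25-point difference (160 and 164). But 85% is the only PASI 50 value given, and 70% v 40% is the row on which the claim rests.

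A reader might go further and infer that dropout before Week 16 erodes the pool again, so that the margin vanishes with any loss. The documents do not support this. The plan's rule for missing binary data is non-responder imputation (Protocol 7.5, SAP 10.1.4). If the 45% and 85% were defined that way among all randomised patients, early dropouts already sit in the 15% below PASI 50, and deducting them again would count them twice. The basis of the rates is not stated. Even on the other reading, a 5% loss at the 45% rate leaves 114 patients and 90.7% power. One further route out of the pool is a Week 16 visit after Day 126 (Protocol 4.1.4). The documents give no frequency for it and describe late attendance as rare.

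**Conclusion.** The two rates are unreconciled, and the choice between them decides whether the expected pool meets the plan's own requirement. At the co-primary's 50% the pool is 105, seven short of 112, and power is about 88% rather than above 90%, roughly four points below the 92.1% at 120. This rests on PASI 50 at 85%, Week 44 rates of 70% v 40%, and the pooled formula that reproduces the tables. On the unpooled approximation 105 patients sit almost exactly at 90%.

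It would be wrong to infer that the statement about 120 patients is false, that the trial must enrol more, or that the co-primary is weakened. The first is correct as written. The loss of power is modest and concerns one comparison. Co-primary power is 99.9% at the same 50%. No test, population, estimate or type I error rate changes. The defect is that the claim of adequate Part B power from 300 adalimumab patients does not hold under an assumption made in the same section.

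**What to change.** In Protocol 7.7 and SAP 4.3, either use one adalimumab Week 16 PASI 90 rate for both calculations, or keep the range and state Part B power across it. Suggested text: *With 300 patients on adalimumab and PASI 50 at 85%, about 120 patients will be re-randomised (92% power at 70% v 40%) if 45% reach PASI 90 at Week 16, about 105 (88%) if 50%, and about 90 (83%) if 55%.*

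Add one sentence saying whether the 45% and 85% already count early dropouts as non-responders, so that the reader knows whether any further allowance is needed.

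The cost is a few lines of text and a slightly less favourable Part B power statement. Enrolment, design and analysis stay as they are.
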